10.4 STATISTICAL ANALYSES

10.4.1 General Approach

The DLTs among patients enrolled during the dose escalation phase will be determined and reported at each dose level. In the expansion phase, the fraction of evaluable patients who have achieved threshold drug levels in cycle 2 will be reported.

10.4.2 Analysis of the Primary Endpoints

The DLTs among patients enrolled during the dose escalation phase will be determined and reported at each dose level.

In the expansion phase, the fraction of evaluable patients who meet the endpoint drug level threshold in cycle 2 will be reported along with two-sided 80% and 95% confidence intervals to aid in interpretation of the results.

10.4.3 Analysis of the Secondary Endpoint(s)

The secondary endpoints are the number and description of adverse events by grade in the expansion cohort. For both dose escalation and expansion cohorts secondary endpoints include: the LMB-100 peak serum level and half-life and AUC during cycle 1. Each of these will be reported using descriptive measures such as percentages and counts as appropriate. For both dose escalation and dose expansion cohorts, we will report the percentage of patients who have formation of neutralizing anti-LMB-100 ADAs affecting drug concentration during cycle 2 and cycle 3.

10.4.4 Safety Analyses

Safety will be evaluated during the dose escalation phase and will include reporting toxicities by grade and type at each dose level in addition to DLTs.

During the 15-patient expansion cohort, the following rule will be used: Within the initial 6 patients, no more than 1 patient in 6 is permitted to experience a DLT attributable to study agents. After the initial 6 patients, safety will be monitored continuously per the following rule: if the cumulative fraction of patients enrolled who experience a DLT attributable to study agents is 1/6 or less, patients will be allowed to continue to enroll onto this protocol.

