1.2.13 Rationale for the combination of LMB-100 with tofacitinib

Efficacy of LMB-100 is limited by the formation of ADAs in approximately half of patients before the 2nd cycle of treatment can be administered and almost all patients before a 3rd cycle. Tofacitinib is an FDA approved drug for the treatment of several autoimmune disorders. Based on the preclinical data on the combination of LMB-100 and tofacitinib described in Section **1.2.10**, we hypothesize that co-administration of tofacitinib with LMB-100 will prevent or delay the formation of high titer ADAs to LMB-100, such that more than 2 effective cycles of immunotoxin can be administered to patients. The goal of this clinical trial is to assess the combination for 1) safety and tolerability and 2) immunogenicity.

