3.1.1 Dose Limiting Toxicity

For the study, a DLT will be defined as any of the following events occurring during the first cycle of treatment (21 days), the DLT evaluation period. Toxicities determined to be unequivocally related to disease progression or intercurrent illness will not be regarded as DLTs. The following will be considered DLTs:

- Any death not clearly due to the underlying disease or extraneous causes
- Transaminitis that meets criteria for Hy's Law: grade ≥2 elevation of AST or ALT with simultaneous elevation of total bilirubin to ≥ 2x ULN while alkaline phosphatase remains < 2x ULN.

Hematological toxicities:

- Grade 4 neutropenia (i.e. absolute neutrophil count (ANC) <0.5 x 10^3 cells/µL for a minimum duration of 7 days)
- Grade 3 and 4 febrile neutropenia (i.e. ANC < 1.0×10^3 cells/µL with a single temperature of >38.3°C or a sustained temperature of ≥38°C for more than one hour; or life-threatening consequences with urgent intervention indicated)
- Grade 4 thrombocytopenia ($\leq 25.0 \times 10^3 \text{ cells/}\mu\text{L}$)
- Grade 3 thrombocytopenia associated with bleeding episodes
- Grade 4 anemia

$\underline{\text{Grade} \geq 3 \text{ non-hematological toxicity with the exception of:}}$

- Grade 3 nausea and vomiting lasting <48 hours occurring in the absence of appropriate anti-emetic treatment
- Grade 3 diarrhea lasting for ≤ 2 days with no fever or dehydration
- Infusion-related reactions up to and including Grade 3. IRRs are not considered to be DLTs since, based on experience with monoclonal antibodies, they are idiosyncratic and not dose-related events. Precautions will be taken if IRRs Grade ≥2 occur (see Section 3.3).
- Asymptomatic grade 3 elevation of ALT, AST, GGT, bilirubin or alkaline phosphatase attributable to study drug that persists for less than 7 days if not violating Hy's Law. (Please note that all grade 4 elevations in these parameters should be considered a DLT)
- Asymptomatic laboratory values (other than ALT, AST, GGT, bilirubin, alkaline phosphatase or creatinine) of Grade 3 that are judged not clinically significant by the investigator.
- Isolated Grade 3 fever (without signs and/or symptoms of an infection) occurring within 48 hours after LMB-100 infusion and resolving within 48 hours to \leq Grade 2 and fully resolved within 1 week.

Other toxicities:

- Any other drug related toxicity considered significant enough to be qualified as a DLT in the opinion of the principal investigator.

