- Inability to start cycle 2 within 2 weeks after completing cycle 1 due to drug-related adverse events.

If a participant experiences a DLT of any grade, the investigator will have the option to either stop treatment or to resume the treatment at the next lowest dose level based on best clinical judgment. Patients will be assessed based on the original cohort. This can be done to allow participants who could potentially benefit from LMB-100 to remain on the study drug treatment, if considered the most beneficial therapeutic option for the participant while managing and monitoring the participant's safety risks.

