7.4.2 Safety Monitoring Committee (SMC)

This protocol will protocol will be periodically reviewed by an intramural Safety Monitoring Committee (SMC). Initial review will occur as soon as possible after the annual NIH Intramural IRB continuing review date.

Subsequently, each protocol will be reviewed every 6 months as the quarterly meeting schedule permits or more frequently as may be required by the SMC based on the risks presented in the

study. For initial and subsequent reviews, protocols will not be reviewed if there is no accrual within the review period.

The SMC review will focus on unexpected protocol-specific safety issues that are identified during the conduct of the clinical trial.

Written outcome letters will be generated in response to the monitoring activities and submitted to the Principal investigator and Clinical Director or Deputy Clinical Director, CCR, NCI.

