7.4.3 Independent Monitoring Committee (IMC)

The protocol will also have an Independent Monitoring Committee (IMC), consisting of the Principal Investigator and two independent, qualified investigators who are outside of the Laboratory of Molecular Biology (LMB) branch and are not involved in the study. The committee will meet after the first 5 subjects have been treated and completed the DLT evaluation window. The IMC will review adverse events and other associated safety data (this review may occur prior to the first annual continuing review date). The committee will be responsible for deciding whether treatment can proceed under the current protocol, whether protocol modifications are required for study continuation, or whether the protocol should be closed to further accrual due to toxicity of the study agents. The IMC may be convened for an ad hoc evaluation of protocol safety by the Principal Investigator or at the request of the IRB or SMC at other occasions during the study if concerns about study drug or research protocol safety or toxicity arise.

The minutes of the IMC meetings will be submitted to the IRB at the time of continuing review, unless an issue arises that requires prompt reporting to the IRB and then results will be submitted more expeditiously.

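### The expansion's only numerical safety rule counts cycle 1 events, so severe attributable toxicity first arising in cycle 2 or 3 cannot trigger it, although the trial aims to create exposure there

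*Combined protocol and SAP*

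**What the plan says.** Section 10.4.4 sets the safety rule for the expansion cohort in two steps. First: "Within the initial 6 patients, no more than 1 patient in 6 is permitted to experience a DLT attributable to study agents". After that, patients may continue to enrol "if the cumulative fraction of patients enrolled who experience a DLT attributable to study agents is 1/6 or less". Section 10.4.4 gives no time window of its own.

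The window comes from section 3.1.1, which defines a DLT for the whole study as "any of the following events occurring during the first cycle of treatment (21 days), the DLT evaluation period". The item in that list that comes nearest to a later cycle is "Inability to start cycle 2 within 2 weeks after completing cycle 1 due to drug-related adverse events". It concerns recovery from cycle 1, not toxicity that begins in cycle 2.

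The aim of the combination, in section 1.2.13, is to hold back antibody formation "such that more than 2 effective cycles of immunotoxin can be administered to patients". Section 10.2 targets 80% of patients at threshold drug level in cycle 2. Three cycles are planned, and section 3.1.3 allows more.

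On oversight, section 7.4.3 schedules one Independent Monitoring Committee (IMC) meeting: "The committee will meet after the first 5 subjects have been treated and completed the DLT evaluation window". Further meetings are ad hoc. For the Safety Monitoring Committee (SMC), section 7.4.2 says: "Initial review will occur as soon as possible after the annual NIH Intramural IRB continuing review date". Reviews then follow about every six months, or more often if the SMC requires.

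**The concern.** A rule based on cycle 1 suits a drug whose later cycles resemble the first or deliver less. Here the intended change lies in the later cycles. Without tofacitinib, antibodies removed much of the drug exposure after cycle 1. If tofacitinib works, more patients will receive effective drug in cycle 2 and, for the first time in any number, in cycle 3. Experience of repeated effective exposure is thin, and the numerical safety rule stops counting just before it begins.

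The plan is also asymmetric. Its futility rule (sections 10.2 and 10.4.6) acts on cycle 2 drug levels, but nothing numerical acts on cycle 2 toxicity. At stake is whether a cluster of severe attributable events after day 21 would bring a prompt, obligatory look at the study, or would depend on someone choosing to call one.

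**Working it through.** **The plan's own figures.** The plan gives no operating characteristics for the safety rule. The decision rule for which it states probabilities is 11 or more of 15 at threshold (section 10.2). By exact binomial:
- at 50%: (1365 + 455 + 105 + 15 + 1)/32768 = 1941/32768 = 5.92%, stated as 5.9%;
- at 80%: 83.58%, stated as 83.6%.

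Both reproduce, so the same method is used below.

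**Earlier exposure (Table 6).**
- Cycle 2: 6 + 5 + 3 + 5 = 19 of 39, or 48.7%. So 20 of 39 (51.3%) lacked expected levels.
- Cycle 3: the printed total is 1 of 13 (7.7%). The printed rows sum to 2 of 15 (13.3%), a mismatch that may come from text extraction. Either way, most lacked expected levels: 12 of 13 (92.3%) or 13 of 15 (86.7%).
- In 15 evaluable patients, 49% is 15 × 0.49 = 7.35 patients with cycle 2 exposure, and the 80% target is 15 × 0.80 = 12. This treats the expected level of Table 6 and the threshold of section 10.1.1 as comparable.

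**The boundary.** 2/11 = 0.182 exceeds 1/6, and 2/12 equals 1/6 and does not. So the rule is crossed at 2 affected patients among up to 11 enrolled, and at 3 among 12-15.

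**Chance of crossing by 15 patients.** Let p be the per-patient event probability, X the number affected among the first 11 and Y the number among the next 4:

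P = P(X ≥ 2) + P(X = 1) × P(Y ≥ 2) + P(X = 0) × P(Y ≥ 3)

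- p = 5%: 0.1019 + 0.3293 × 0.0140 + 0.5688 × 0.0005 = 0.107
- p = 10%: 0.3026 + 0.3835 × 0.0523 + 0.3138 × 0.0037 = 0.324
- p = 20%: 0.6779 + 0.2362 × 0.1808 + 0.0859 × 0.0272 = 0.723

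**Cycle 1 only against cycles 1-3.** The documents give no event rates by cycle, so these are assumed. With cycle 1 rate c and late rate l among patients without a cycle 1 event, the rule as written uses p = c. Counting all three cycles uses p = 1 − (1 − c)(1 − l).

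| c | l | p over cycles 1-3 | Rule as written | Same boundary, cycles 1-3 |
|---|---|---|---|---|
| 5% | 0% | 5.0% | 10.7% | 10.7% |
| 5% | 10% | 14.5% | 10.7% | 52.5% |
| 5% | 20% | 24.0% | 10.7% | 82.5% |
| 5% | 30% | 33.5% | 10.7% | 95.3% |
| 10% | 10% | 19.0% | 32.4% | 69.2% |
| 10% | 20% | 28.0% | 32.4% | 89.6% |
| 10% | 30% | 37.0% | 32.4% | 97.4% |

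For a given cycle 1 rate, the fourth column does not move with the late rate. The last column is an upper bound for timely action, because late events are seen after further patients have enrolled.

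**The case against.** The strongest reply is that later toxicity is far from unwatched. Sections 3.3 and 3.5 hold or end an individual's treatment in any cycle. Section 10.2 lets the investigator take a dose below the MTD into the expansion if chronic toxicity is judged intolerable. Adverse events are followed through treatment and for 30 days after, and serious ones reach the sponsor within 24 hours. The team meets weekly, and the IMC can be convened ad hoc and can close accrual. All of this stands. A reader might infer that nothing in the plan reacts to toxicity after cycle 1, and that would be wrong. What is missing is narrower: a numerical study-level trigger.

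Four other strong readings also go beyond the documents.
- A reader might infer that the 1/6 rule would certify the dose as safe. No section says so. The positive-outcome rule concerns drug levels, and adverse events by grade are a secondary endpoint with no cycle limit.
- A reader might infer that nearly all patients could be enrolled before the first SMC review. Section 10.2 gives up to two per month and about two years for a ceiling of 45. Twelve months would give about 24 of 45, or 24 × 27/45 = about 14 of the 27 evaluable. The review date follows the IRB calendar, so even 12 months is an assumption.
- A reader might infer that cycle 2 exposure is largely new. About half of earlier patients had it, and section 1.2.8.1.3 says most patients without pre-existing antibodies reached effective levels for two cycles. The contrast is sharp only for cycle 3.
- A reader might infer that cumulative toxicity is to be expected. The documents support only that it could occur. The serum half-life is 61 minutes, and monkeys showed no accumulation over two cycles. Any half-life prolongation by tofacitinib, seen in mice, would act from cycle 1 and so fall inside the DLT window.

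Finally, section 10.2 expects as many as 50% of patients to progress by restaging after 2 cycles. That shrinks the number at risk in cycle 3 and lowers the late rate per enrolled patient.

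**Conclusion.** The point holds in its narrow form. The only prespecified study-level safety rule in the expansion cannot be triggered by severe attributable toxicity that first arises in cycle 2 or 3. The existing safeguards for those cycles act on individuals or at discretion, and the one scheduled IMC meeting is tied to the cycle 1 window.

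This is a gap in design, not a contradiction or a calculation error. Its size depends on event rates that the documents do not give. With a 5% cycle 1 rate and a 10% to 30% late rate, the rule as written stays at 10.7%, against 52.5% to 95.3% if the same boundary covered all three cycles. Those figures assume independent patients and late rates expressed per enrolled patient free of a cycle 1 event. Drop-out before cycles 2 and 3 would reduce the contrast. The case for change rests on the low cost of closing the gap, not on evidence that late toxicity will be common.

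**What to change.** Leave the cycle 1 rule in section 10.4.4 unchanged and add to that section:
- Attributable events that meet the section 3.1.1 severity criteria in any of cycles 1-3 are counted once per patient.
- When at least 2 patients are affected and the cumulative fraction exceeds 1/6 (2 or more among up to 11 enrolled, 3 or more among 12-15), an IMC review is mandatory. This is a review trigger, not an automatic stop. If replacements under section 10.3.1 take enrolment past 15, the same fraction applies.
- These events are reported by cycle, with the number of patients treated in each cycle as denominator.

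The text should also say whether enrolment continues while the review is awaited, as section 10.4.6 does for the futility look.

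The minimum of 2 patients matters. Without it, one event among the first five would exceed 1/6, and at a 10% three-cycle rate that alone would occur with probability 1 − 0.9^5 = 41%. With it, a review is called by 15 patients with probability about 11%, 32% and 72% at assumed three-cycle rates of 5%, 10% and 20%.

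The cost is a few sentences in an amendment, a possible extra IMC meeting and a short enrolment pause. The adverse event data are already collected and the committee already exists. No dose, schedule or patient-level treatment rule changes.

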10.4.5 Baseline Descriptive Statistics

Demographic and clinical characteristics of all patients will be reported.

10.4.6 Planned Interim Analyses

As an early stopping rule, if after the first 5 evaluable patients have been treated, 0 of the 5 meet threshold drug levels in cycle 2, then no further patients will be accrued since this is inconsistent with the goal of having 11 or more of 15 meeting threshold drug levels. Accrual will not be halted while awaiting the determination of drug levels in cycle 2 based on 5 patients; thus, additional patients may begin treatment while this determination is being made.

10.4.7 Sub-Group Analyses

In the expansion cohort, the fraction of patients meeting threshold drug levels in cycle 2 will be analyzed as an exploratory endpoint according to pancreatic adenocarcinoma vs. extra-hepatic cholangiocarcinoma history.

10.4.8 Tabulation of individual Participant Data

None will be provided

10.4.9 Exploratory Analyses

The following are the intended exploratory analyses focusing on the patients in the expansion cohort:

Disease control rate (DCR) at 9 weeks will be estimated along with a 95% confidence interval. PFS and OS will be estimated by the Kaplan-Meier method, along with 95% confidence intervals. Changes in appropriate tumor markers with treatment (if applicable to patient's tumor type) will be determined and tested for change from baseline using a Wilcoxon signed rank test. Titer of free anti-LMB-100 antibodies at the start of each cycle and following completion of treatment will be obtained and results reported descriptively; the relationship of these values with peak serum drug levels of LMB-100 will be explored. Association of response with tumor MSLN expression will be done by comparing levels between responders and non-responders using an appropriate nonparametric test such as a Cochran-Armitage test or Fisher's exact test. Changes in circulating endothelial cells following immunotoxin treatment, changes in serum cytokines following immunotoxin treatment, and changes in tumor microenvironment following immunotoxin treatment will be reported descriptively, with statistical testing of changes as appropriate. Any statistical tests performed on the exploratory endpoints will have results presented without formal adjustment but interpreted in the context of the number of tests performed. In patients receiving treatment extension, the anti-drug antibodies and peak plasma LMB-100 drug levels will be obtained at each cycle after cycle 3 and reported with descriptive statistics. The levels of these

measures after cycle 3 may be compared descriptively to those in earlier cycles for purposes of evaluating the effect of the agent in this small subset of patients.

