1.1.3 Exploratory Objectives

- To obtain preliminary assessment of activity including change in appropriate serum tumor markers with treatment, objective response rate (ORR), disease control rate after 3 cycles (~9 weeks) of treatment (DCR), progression free survival (PFS) and overall survival (OS)
- Evaluate association between anti-LMB-100 antibody titer and peak serum drug level
- To examine the relationship between MSLN expression and response to treatment
- To evaluate changes in the tumor microenvironment following treatment with LMB-100 plus tofacitinib
- To assess changes in circulating immune cell and cytokine levels caused by the treatment
- For treatment extension: To determine whether to facitinib can continue to prevent ADA formation beyond 3 cycles of treatment regardless of whether patients had another intervening therapy or not.

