1.2.8.2.2 Combination of LMB-100 with nab-paclitaxel

The LMB-100 has also been tested in both mesothelioma (NCT02798536) and pancreatic cancer patients (NCT02810418) in combination with nab-paclitaxel. In mesothelioma patients, nab-paclitaxel was given at a dose of 100 mg/m² on Days 1 and 8. MTD of LMB-100 was found to be 100 mcg/kg/day given over 30 minutes on days 1, 3 and 5 of each 21-day cycle. In pancreatic adenocarcinoma patients, nab-paclitaxel was given at a dose of 125 mg/m² on Days 1 and 8. At 100 mcg/kg, DLT of grade 3 myalgia was observed in 2/6 patients. A reduced dose of 65 mcg/kg/day was subsequently tested. DLT of grade 3 edema associated with vascular leak was observed in 1/6 evaluable patients making this the MTD of LMB-100 for the combination. At the MTD, 1/14 patients experienced a partial response as their best response following the maximum 2 cycles of treatment. Grade 4 vascular leak associated with ventricular dysfunction was observed in one patient and the study was closed to further accrual. ADA development is shown in Table 6, and was similar to the Roche trial of single agent LMB-100. Evaluation of this combination continues in pancreatic adenocarcinoma patients (manuscripts in preparation).

Number of patients with expected serum LMB-100 level							
Treatment	Study	Tumor Type	C2	C3			
single agent	Roche	MSLN(+)	6 of 9	1 of 3			
single agent	NCI	mesothelioma	5 of 10	0 of 9			
+NAB-paclitaxel	NCI	mesothelioma	3 of 10	0 of 0			
+NAB-paclitaxel	NCI	PDAC	5 of 10	1 of 3			
		TOTAL	19 of 39	1 of 13			
			49%	8%			

Table 6.	ADA dev	elonment	during l	[MR_100	treatment
	ADA UCV	ciopinent	uuring i		ti catinent

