2 ELIGIBILITY ASSESSMENT AND ENROLLMENT

2.1 ELIGIBILITY CRITERIA

2.1.1 Inclusion Criteria

- 2.1.1.1 Patients must have histologically confirmed solid tumor malignancy for which no curative therapy exists.
- 2.1.1.2 Pancreatic adenocarcinoma, extrahepatic cholangiocarcinoma or epithelioid subtype of mesothelioma, as determined by NCI Laboratory of Pathology, OR for all other tumor types, at least 20% of tumor cells must express mesothelin. Determination can be made using archival tumor tissue or fresh biopsy if archival tumor tissue is not available.
- 2.1.1.3 All patients must have evaluable disease (i.e. measurable per RECIST 1.1. or by following CA19-9 tumor marker). Patients in the expansion cohort must have measurable disease, per RECIST 1.1. See Section 6.3 for the evaluation of measurable disease.
- 2.1.1.4 Patients must have received at least one prior standard systemic treatment regimen for advanced disease OR be ineligible to receive available standards due to co-morbidities, prior toxicity, lack of standard options for tumor type, or having received all standards

available for prior treatment of early stage disease OR have refused first-line standard systemic treatment but have received prior anti-cancer treatments.

- 2.1.1.5 Patients with dMMR/MSI-H disease must have received at least one prior anti-PD1 therapy, be ineligible to receive this treatment due to concurrent medical conditions, or have refused this therapy.
- 2.1.1.6 ECOG performance status (PS) 0-2 (Appendix A- Performance Status Criteria).
- 2.1.1.7 Age ≥18 years. Because no dosing or adverse event data are currently available on the use of LMB-100 alone or in combination with tofacitinib in persons with <18 years of age, children are excluded from this study.
- 2.1.1.8 Patients must be more than 14 days removed from most recent minor surgical procedure (such as biliary stenting), 28 days from most recent major surgical procedure and 14 days from radiation therapy, systemic treatments (such as chemotherapy), or experimental drug treatment. All acute toxicities from prior treatment must have resolved to grade 1 or less except alopecia, anemia, peripheral neuropathy, or endocrinopathies corrected by replacement therapy.
- 2.1.1.9 Adequate hematological function: neutrophil count of $\ge 1.5 \times 10^3$ cells/µL, platelet count of $\ge 85,000/\mu$ L, hemoglobin ≥ 9 g/dL
- 2.1.1.10 Serum albumin \geq 2.5 mg/dL without intravenous supplementation

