This evaluation in 15 patients of either histology (but at least 8 patients in this expansion phase must have pancreatic adenocarcinoma) will be undertaken using the following guidelines: The objective will be to determine if the fraction of patients who are able to achieve threshold levels of LMB-100 in cycle 2 is consistent with 80% and greater than 50%. If 15 evaluable patients are enrolled, and if 11 or more patients meet threshold drug levels in cycle 2, then the probability of this occurring is 5.9% if the true probability of achieving threshold drug levels in cycle 2 were 50% and the probability of this occurring is 83.6% if the true probability of achieving threshold drug levels in cycle 2 were 80%. Thus, the expansion phase would be considered to have a positive outcome if 11 or more of 15 patients in the expansion phase achieve threshold drug levels. In practice, after the trial has ended accrual, the fraction of evaluable patients assessed during the expansion phase that achieve threshold drug levels in cycle 2 will be determined and reported along with two-sided 80% and 95% confidence intervals to aid in interpretation of the results. The fraction of patients who achieve threshold drug levels in cycle 3 will also be reported along with a 95% confidence interval, but this may be a small fraction and will be interpreted as being an exploratory evaluation.

As an early stopping rule, if after the first 5 evaluable patients in the expansion cohort have been treated, 0 of the 5 achieve threshold drug levels in cycle 2, then no further patients will be accrued as soon as that can be determined, with no pause in accrual, since this would be inconsistent with the goal of having 11 or more of 15 patients achieving threshold drug levels in cycle 2.

With up to 12 patients in the dose escalation phase and 15 in the expansion cohort, a maximum of 27 evaluable patients are required to complete accrual to this study. The accrual ceiling will be set at 45 patients to account for screen failures or patients who are treated but unable to complete the DLT period. It is anticipated that up to two patients per month may enroll onto this trial. Thus, accrual is expected be completed in approximately 2 years.

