10.3 POPULATIONS FOR ANALYSES

10.3.1 Evaluable for toxicity

All patients who receive treatment during dose escalation will be reported. Any patient who receives any study drug treatment and experiences a DLT related to study drug within 21 days of initial treatment is evaluable. Otherwise, patients evaluable for DLT must: 1) receive all doses of study drugs, 2) be followed for study drug toxicity for at least 21 days after the administration of the first dose of LMB-100.

In the expansion phase, up to 15 evaluable patients who can have their drug levels assessed in cycle 2 will be included in analyses. Up to 5 patients will be replaced if they have PD before C2, but if more than 5 patients progress before C2, then no further patients will be accrued as soon as this can be determined.

10.3.2 Evaluable for objective response:

Only those patients who have measurable disease present at baseline, have received at least one cycle of therapy, and have had their disease re-evaluated will be considered evaluable for response. These patients will have their response classified according to the definitions stated below. (Note: Patients who exhibit objective disease progression prior to the end of cycle 1 will also be considered evaluable.) Responses or progressions noted in patients receiving treatment extension will be recorded in the study database but will not be reported in the aggregate objective response rate, which only corresponds to assessments taken prior to the start of a 4th cycle.

10.3.3 Evaluable Non-Target Disease Response:

Patients who have lesions or tumor marker present at baseline that are evaluable but do not meet the definitions of measurable disease, have received at least one cycle of therapy, and have had their disease re-evaluated will be considered evaluable for non-target disease. The response assessment is based on the presence, absence, or unequivocal progression of the lesions or increase in tumor marker.

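### The MSLN analysis in 10.4.9 uses response only as responder versus non-responder; with about 15 patients and few responders it may say little, and a Spearman correlation with tumour shrinkage would be a cheap addition

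*Combined protocol and SAP*

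**What the plan says.** Section 1.1.3 lists an exploratory objective: "To examine the relationship between MSLN expression and response to treatment". Section 10.4.9, "focusing on the patients in the expansion cohort", gives the method: the association "will be done by comparing levels between responders and non-responders using an appropriate nonparametric test such as a Cochran-Armitage test", or Fisher's exact test. No other MSLN-response analysis is described.

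Section 10.4.9 does not define a responder. Section 6.3.6 counts PR and CR as objective response, and Section 6.3.3.1 sets PR at a decrease of at least 30% in the sum of target-lesion diameters. Section 10.4.9 states no alpha or power for exploratory tests. It says that results will carry no formal adjustment and will be read in light of how many tests were done.

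The data for a finer analysis are largely planned. Section 2.1.1.3 states "Patients in the expansion cohort must have measurable disease, per RECIST 1.1", Section 6.3.1 has target-lesion diameters measured and summed at baseline, and Section 5.1.5 plans retrospective MSLN IHC on leftover tissue. For eligibility, MSLN is scored as a percentage of tumour cells (Section 2.1.1.2).

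**The concern.** Tumour shrinkage is measured on a continuous scale, but the plan keeps only which side of a 30% cut each patient falls on. If few patients respond, nearly everyone is in one group and the comparison carries little information about MSLN. With no responder there is nothing to compare. With one, the result rests on a single patient.

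MSLN is the target of LMB-100, and Section 11.1 calls the drug ineffective against cells that lack it. The relation between expression and tumour change is therefore worth estimating as well as 15 patients allow. The same patients will usually have lesion sums that order them by degree of shrinkage or growth, and the analysis does not use that ordering.

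**Working it through.** **Inputs from the documents**
- Expansion cohort: 15 evaluable patients (Section 10.2). Up to 20 may be treated, since "Up to 5 patients will be replaced if they have PD before C2" (Section 10.3.1).
- Response rate: "1/14 patients experienced a partial response as their best response" (Section 1.2.8.2.2), from LMB-100 with nab-paclitaxel, at most 2 cycles, in pancreatic cancer. 1/14 = 7.1%, exact 95% CI 0.2% to 33.9%.
- Other rates, as sensitivity values only: 17% and 23% for chemotherapy in pancreatic cancer (Section 1.2.1), and 3/10 for an earlier immunotoxin with immune suppression in mesothelioma (Section 1.2.3.1). A rate of 10% is added as an intermediate value.

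**Assumptions not in the documents:** two-sided alpha 0.05, and the correlations used in the simulation.

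**The plan's own figure.** The documents give no figure for the MSLN analysis. The sizing rule for the 15 patients (11 or more successes) reproduces by exact binomial: 0.0592 at 50% and 0.8358 at 80%, against the stated 5.9% and 83.6%.

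**Step 1: number of responders, X ~ Binomial(15, p).** At p = 1/14:
- P(X=0) = (13/14)^15 = 0.329
- P(X=1) = 15 × (1/14) × (13/14)^14 = 0.380
- P(X≤1) = 0.709

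At other rates P(X≤1) is 54.9% (10%), 24.9% (17%), 10.9% (23%) and 3.5% (30%). With n=20 and p = 1/14 it is 57.7%. P(X≤1) exceeds one half only if the true rate is below about 10.9% at n=15, or about 8.3% at n=20.

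**Step 2: smallest attainable p.** With X=0 no test exists. With X=1 and an MSLN group of m patients, the chance that the responder falls in that group is m/15. The smallest Fisher p is therefore at m=1:
- Fisher, n=15: 1/15 = 0.067
- Fisher, n=20: 1/20 = 0.05, still not below 0.05
- Exact Cochran-Armitage, n=15: at best 0.067
- Exact rank-sum, n=15: 2/15 = 0.133

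The large-sample Cochran-Armitage test behaves differently. Its statistic is N × r². For one responder in the smaller group of a 12/3 split it is 15 × 12²/(3 × 12 × 1 × 14) = 4.286, p = 0.038. For 13/2 it is 15 × 13²/(2 × 13 × 1 × 14) = 6.964, p = 0.008. For 5/5/5 categories, p = 0.20.

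**Step 3: a near-median MSLN split (7/8), as an illustration.** With 3 responders the smallest Fisher p is 0.077; with 4 it is 0.026. At least 4 responders are needed. P(X≥4) is 1.9% at 1/14 and 24.3% at 17%, so p<0.05 is out of reach in about 98% and 76% of cohorts.

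**Step 4: what the full scale recovers.** Simulation with n=15, bivariate normal MSLN and shrinkage, and the responder cut set to give the stated rate. Power at two-sided 0.05:
- Correlation 0.3: Spearman about 17%; rank-sum of MSLN by responder status about 3% (rate 1/14) and 7% (rate 17%)
- Correlation 0.6: Spearman about 62%; rank-sum about 9% and 25%

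Repeat runs differ by a point or two. Spearman was ahead in every setting run, by about 10 points at correlation 0.3 and rate 17% (17 − 7), and by about 53 points at correlation 0.6 and rate 1/14 (62 − 9).

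**The case against.** Several points on the other side are fair.

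- **A reader might infer that the named tests cannot reach p<0.05 whatever the data show.** That is true of the exact tests with 0 or 1 responder. It is not true of the large-sample Cochran-Armitage test, which can fall below 0.05 with one responder when the top MSLN category is small. For that test only the zero-responder case (32.9% at 1/14) is impossible. Such a p-value would rest on one patient and an approximation that is not trustworthy there, so it does little to defend the plan.
- **A reader might take 1/14 as this trial's own expected response rate.** The documents state no expected rate for LMB-100 with tofacitinib. The 1/14 comes from another combination limited to 2 cycles, and its interval is wide. At 17% or above, most cohorts would have 2 or more responders.
- **A reader might infer that MSLN must be cut into categories.** The two tests are only examples. Comparing levels with a suitable nonparametric test would allow a rank-sum test on uncategorised MSLN, which is why the power comparison above uses it.
- **The analysis is exploratory.** No endpoint, dose decision or stopping rule depends on it, and p<0.05 is a yardstick brought in here. Nothing in the plan says that a non-significant result would be reported as no association.
- **The planned comparison does answer the stated objective.** Percent change is a different measure and misses progression by new lesions unless a convention covers it.
- **The gain is not uniformly large.** At correlations of 0.4 or below, Spearman's own power is under 30%. If tissue is missing and n falls to 10, it is about 40% at correlation 0.6 and 20% at 0.4.

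These points limit the claim and lower its weight. They do not change the fact that responder status is the only form of response that the analysis uses.

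**Conclusion.** The point stands as a cheap improvement to an exploratory analysis. Section 10.4.9 leaves the test open but fixes the responder split. If the true response rate is near the cited 1/14, about 71% of 15-patient cohorts (58% with 20) would have 0 or 1 responder, and exact tests could not then reach two-sided p<0.05. The share falls to 55% at a 10% rate and 25% at 17%, so the problem is likely only if the true rate is below about 11%.

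The case for the added analysis depends less on that rate. Spearman on the full scales had more power than the responder-based rank-sum test at every setting run, but the size of the gain rests on assumed correlations, normal data and complete MSLN results. With about 15 patients either analysis gives an imprecise answer, so the value lies mainly in the estimate and its interval.

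**What to change.** In Section 10.4.9, keep the responder comparison and add beside it a Spearman rank correlation with 95% CI between MSLN expression and best percent change from baseline in the sum of target-lesion diameters, reported as an exploratory estimate. Specify:

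- MSLN as percent positive tumour cells, or the ordinal IHC score if that is what is recorded (Section 5.1.5 does not say).
- Patients with objective progression, including by new lesions, before any usable post-baseline sum are ranked as worst.
- The number of patients with MSLN data is stated.

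The cost is a few sentences and one extra convention. No new procedure is needed, because measurable disease, lesion sums and MSLN IHC are already in the protocol. The downside is a smaller n, and a wider interval, if leftover tissue is missing for some patients.
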